4.3. Primary Efficacy Population.....	24
4.4. Evaluable Population	25
4.5. Induction Phase Dosing Compliant Population.....	25
4.6. Study Dosing Compliant Population	25
5. STATISTICAL METHODS	25

5.1. Subject Disposition, Demographic, and Baseline Characteristics	25
5.2. Efficacy Analysis	25
5.2.1. Primary Efficacy Endpoint.....	25
5.2.2. Primary Efficacy Analysis.....	26
5.2.3. Sensitivity Assessments for the Primary Efficacy Analysis.....	27
5.2.4. Additional Efficacy Endpoints	27
5.2.5. Additional Efficacy Analyses.....	27
5.2.6. Subgroup Analyses.....	27
5.3. Safety.....	27
5.3.1. Adverse Events.....	27
5.3.2. Study Drug Exposure and Concomitant Medications	28
5.3.3. Clinical Laboratory Assessments	28
5.3.4. Other Safety Analyses.....	28
6. PROTOCOL DEVIATIONS	29
7. CHANGES IN THE PLANNED ANALYSES	29
8. REVISION HISTORY	30
9. PROGRAMMING CONVENTIONS	31
10. PROPOSED TABLES, LISTINGS, AND FIGURES DSMB ANALYSES.....	33
11. PROPOSED TABLES, LISTINGS, AND FIGURES 6 MONTH ANALYSIS.....	35
12. PROPOSED TABLES, LISTINGS, AND FIGURES FINAL ANALYSIS.....	37

1 **INTRODUCTION**

This document describes the statistical methods and data presentations to be used in the summary and planned analysis of data from Protocol VB4-845-02-IIIA. Background information is provided for the overall study design and objectives. The reader is referred to the study protocol and case report forms (CRFs) for details of study conduct and data collection. Analyses of pharmacokinetic, EpCAM, and anti-Vicinium antibody data will be described in a separate Analysis Plan.

This analysis plan will serve as the final documentation for the planned statistical analyses for study VB4-845-02-IIIA and will supersede the protocol if there are any discrepancies.

1.1. **STUDY OVERVIEW**

This is an open-label, non-randomized, multicenter, multiple-dose, study of Vicinium in approximately 134 subjects with non-muscle invasive bladder cancer (NMIBC). Subjects will have histologically-confirmed non muscle-invasive carcinoma in situ (CIS) and/or papillary disease (high grade non-invasive papillary carcinoma (Ta) or any grade in which the tumor invades lamina propria (T1)) of the bladder who failed previous treatment (i.e., not those who are intolerant) with bacillus Calmette-Guérin (BCG).

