3.3.5. Imputation of Incomplete Dates

An incomplete date occurs when the exact date an event occurred or ended cannot be obtained from a subject. The database contains data fields for month, day, and year. A date is incomplete if at least one of these three fields is not known. For many of the planned analyses, a complete date is necessary in order to determine if the event should be included in the analysis (i.e., if the event is treatment-emergent) or to establish the duration of an event. In such cases, incomplete dates will be imputed.

For purposes of imputation of dates for adverse events and concomitant medications, the start and stop dates of study drug will be utilized to impute missing event start and stop dates. All events with an incomplete start/onset date are assumed to have started at the initiation of the study drug. All events with an incomplete end/resolution date are assumed to have ended on the last date of study drug. The missing or incomplete dates will be imputed using the algorithm described in Table 1.

In an effort to minimize bias, the project statistician will impute missing or incomplete dates from forms other than the adverse events or concomitant medications in a systematic, reasonable manner. In these cases, missing date portions will be imputed using available data as described in Table 2.

Table 1. Algorithm for Imputing Missing/Incomplete Onset or Resolution Dates for Adverse Events or Concomitant Medications

Description of Missing/Incomplete Data Piece	Algorithm	Example
Completely Missing Start Date	Use Study Drug Start Date	Original Event Start Date = " " Study Drug Start Date = "04-16-2014" Imputed Event Start Date = "04-16-2014"
Incomplete Start Date - Missing Day Part	Use Day Part of Study Drug Start Date	Original Event Start Date="04- -2014" Study Drug Start Date="04-16-2014" Imputed Event Start Date="04-16-2014"
Incomplete Start Date - Missing Day/Month Part	Use Day/Month Part of Study Drug Start Date	Original Event Start Date="2014" Study Drug Start Date="04-16-2014" Imputed Event Start Date="04-16-2014"
Completely Missing Stop Date	Use Study Drug Stop Date	Original Event Stop Date = " " Study Drug Stop Date = "04-16-2014" Imputed Event Stop Date = "04-16-2014"
Incomplete Stop Date - Missing Day Part	Use Day Part of Study Drug Stop Date	Original Event Stop Date="04- -2014" Study Drug Stop Date="04-16-2014" Imputed Event Stop Date="04-16-2014"

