3.3.7. Definitions and Terminology

Adverse Event

An adverse event (AE) is defined as any unfavorable and unintended sign (including an abnormal laboratory finding), symptom or disease temporally associated with the use of a medical treatment or procedure regardless of whether it is considered related to the medical treatment or procedure (attribution of unrelated, unlikely, possible, probable, or definite).

Any medical condition that is present at the time the subject is screened, but does not deteriorate, should not be reported as an AE. However, if it deteriorates at any time during the study it should be recorded as an AE. Hospitalization for elective treatment of a preexisting condition that did not worsen from baseline is not considered an AE or serious AE (SAE).

The descriptions and grading scales found in the revised National Cancer Institute Common Terminology Criteria for Adverse Events (NCI-CTCAE) version 4.03 will be utilized for AE reporting.

Serious Adverse Event

A serious adverse event is any AE that is fatal, life-threatening, requires or prolongs hospital stay, results in persistent or significant disability or incapacity, results in a congenital anomaly or birth defect, or is an otherwise important medical event.

Treatment-emergent AE

Treatment-emergent AEs (TEAEs) are all AEs occurring on or after the date of first dose of study drug through 30 days post the last dose of study drug.

Baseline Value

For purposes of analysis, the baseline value is defined as the last value obtained prior to the first dose of Vicinium.

Study Drug

For the purposes of this study, the term study drug refers to Vicinium.

Day 1 (Baseline)

Day 1 is the day that the first dose of Vicinium is received.

Age

The age of a subject is defined as (Date of Informed Consent – Date of Birth + 1)/365.25.

Study Day

Study Day is defined relative to Baseline (Day 1). Thus, the study day of an event is calculated as:

$$\text{Study Day} = \text{event date} - \text{date of Day 1} + 1.$$

Change from Baseline

Change from baseline for a given endpoint is defined as the Study Day X value minus the Baseline Value.

Cohort 1 Subjects

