5.3. SAFETY

5.3.1. Adverse Events

Adverse events will be mapped to a Medical Dictionary for Regulatory Activities (MedDRA) version 18.0 or higher preferred term and system organ classification. The severity of all AEs will be assessed

by the investigator according to the protocol and the CTCAE v 4.03 criteria. If a subject experiences multiple events that map to a single preferred term, the greatest severity grade and strongest investigator assessment of relation to study medication will be assigned to the preferred term for the appropriate summaries. Should an event have a missing severity or relationship, it will be classified as having the highest severity and/or strongest relationship for the purposes of summary analyses. For presentation in the data listings, the missing values will be noted. The occurrence of TEAEs will be summarized by phase (induction vs maintenance) using preferred terms, system organ classifications, and severity. Separate summaries of treatment-emergent SAEs, TEAEs related to Vicinium, TEAEs leading to discontinuation of study or study drug, serious TEAEs, and Grade 3 or higher TEAEs will be generated. All AEs reported will be listed for individual subjects showing both verbatim and preferred terms. Missing onset dates will be imputed as previously outlined in Section 3.3.5 as required to determine treatment-emergent events.

Summaries of TEAEs, TEAEs related to Vicinium, Serious TEAEs, and Grade 3 or higher TEAEs will also be presented by each subgroup.

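### The SAP's TEAE definition has no worsening clause, so an AE that starts between consent and first dose, worsens on Vicinium and stays on one record is left out of the TEAE tables

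*SAP*

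**What the plan says.** SAP 3.3.7 (Treatment-emergent AE) reads "Treatment-emergent AEs (TEAEs) are all AEs occurring on or after the date of first dose of study drug" and closes the window 30 days after the last dose. It does not mention severity or change in severity.

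The date that decides is the onset date. SAP 3.3.5 explains that "a complete date is necessary in order to determine if the event should be included in the analysis (i.e., if the event is treatment-emergent", and SAP 5.3.1 repeats that "Missing onset dates will be imputed as previously outlined in Section 3.3.5 as required to determine treatment-emergent events".

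Three other provisions bear on the point:

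- **SAP 3.3.7, Adverse Event.** A condition present when the subject is screened is not an AE while it does not get worse. "However, if it deteriorates at any time during the study it should be recorded as an AE".
- **Protocol 15.2.** Pre-existing conditions that stay stable or improve are recorded but are not TEAEs. Worsening beyond normal fluctuation is an AE.
- **SAP 3.3.7, Treatment-emergent Laboratory Toxicity.** A rise of one grade or more over baseline counts.

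SAP section 1 says that the SAP "will supersede the protocol if there are any discrepancies". SAP section 7 lists one change from the protocol, the primary efficacy population, and says no others have been described.

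**The concern.** Protocol 15.2 withholds TEAE status only from pre-existing conditions that are stable or improve, which implies that those that worsen on treatment should count. The SAP's date-only rule does not carry this over, and the SAP governs where the two differ. It also treats clinical events less strictly than laboratory values, although both are graded on CTCAE 4.03.

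The AE summary tables proposed for the final analysis (SAP section 12) are all titled treatment-emergent, so an event that fails the definition appears in no AE summary table. With a single arm there is no comparator in which the same omission would occur. Where an event is missed, the error can only lower the reported toxicity.

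**Working it through.** The plan gives no figure for this point, so the check is to run the rule on specific cases.

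**Can a record with pre-dose onset exist?** Yes. Protocol 15.1 records AEs from the signing of consent, and screening may last up to 8 weeks (Protocol 10.1). The first scheduled AE assessment is before the first dose in Week 1 (Protocol 10.3.1), and it can pick up an event that began earlier and is still open.

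**Which date decides?** Onset, from SAP 3.3.5 and 5.3.1 as quoted above. The word occurring might be stretched to cover ongoing events, but those two sections tie the decision to the start date.

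**Four illustrative cases** (the days and grades are examples, not data):

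1. Onset on Day −10 at Grade 1, rising to Grade 3 on Day 20, on one record. Onset precedes first dose, so the event is not a TEAE. It is absent from the TEAE and Grade 3 or higher tables, and from the related and serious tables if it qualifies for those. It remains in the listings.
2. The same course, but the site enters the worsening as a new AE with onset on Day 20. It is a TEAE and is tabulated.
3. A condition present at screening that is first reported as an AE when it deteriorates on Day 20, and is dated then. It is a TEAE and is tabulated.
4. Case 1 under a rule that also admits worsening on or after first dose. It is a TEAE and is tabulated at Grade 3.

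Only case 1 is lost, and a worsening clause recovers it.

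**Do the documents rule case 1 out?** No. Neither says whether a rise in grade opens a new record or updates the existing one. The SAP refers the reader to the CRF for data collection, and the CRF is not among the documents.

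**The case against.** The strongest reply is that worsening is already handled in the definition of an AE. Both documents make deterioration of a pre-existing condition an AE in its own right, so a deterioration on drug is an AE with an on-drug onset. If a symptom that arises during screening is read as pre-existing, SAP and protocol agree and there is no discrepancy to resolve. This stands for most worsening, including cases 2 and 3. It does not close case 1, because neither text says that an AE already open must be re-entered when its grade rises.

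Several points limit the reach of the gap, and all of them stand:

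- The loss depends on a record-keeping practice that the documents do not show. AEs are assessed before and after every dose, so many sites may open a new record.
- The Screening and Baseline lists (Protocol 10.1 and 10.2) contain no AE assessment, and Protocol Table 3 schedules none before Week 1.
- Dosing is barred within 2 weeks of a biopsy or TURBT, so some procedure-related symptoms will have settled by Day 1.
- Worsening laboratory values are counted under their own rule.
- Nothing disappears from the report: "All AEs reported will be listed for individual subjects showing both verbatim and preferred terms". The DSMB chair receives every SAE report (Protocol 15.1).

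A reader might go further and infer that the date imputation in SAP 3.3.5, Table 1, adds to the under-count, because a missing day takes the instruction "Use Day Part of Study Drug Start Date" and can therefore fall before dosing. The documents do not support this. With drug start on 16 April 2014, an onset known only as March 2014 becomes 16 March, but every day in March precedes 16 April, so the event is correctly pre-dose. An onset known only to the month or year of first dose becomes the first-dose date and counts as a TEAE. At that boundary the rule leans toward counting toxicity.

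**Conclusion.** The point holds in a narrow form. The SAP's TEAE rule gives a wrong result, in the direction of lower toxicity, for an AE with onset between consent and Day 1 that worsens on Vicinium and is kept as one record. It does not hold for worsening in general.

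The size cannot be computed. The documents do not give the share of subjects with an AE open at Day 1, the chance that such an event worsens, or the share of sites that would keep one record. A reader might be tempted to build an estimate from the Phase 2 dysuria rate or the Phase 2 count of severe events, but neither is a rate of worsening from an already open AE. The effect is probably small. It is confined to the safety tables, and efficacy is unaffected.

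The conclusion rests on reading treatment emergence as an onset-date rule, which the SAP text supports, and on some sites keeping a single record, which is an assumption. This is a cheap improvement, not a defect that threatens the trial's conclusions.

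**What to change.** In SAP 3.3.7, define a TEAE as either:

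- an AE with onset from first dose through 30 days after last dose; or
- an AE with earlier onset that increases in CTCAE grade or becomes serious within that window.

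In the SAP 5.3.1 tables, show events of the second kind at their worst on-treatment grade.

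If the grade at Day 1 or the date of worsening was not kept, query the site. Failing that, count a pre-dose-onset AE that is ongoing at Day 1 as treatment-emergent, whatever its assessed relationship to Vicinium. Treatment emergence should not depend on the causality judgement: otherwise a non-serious rise judged unrelated would still be missed. This follows the SAP's existing approach to gaps: "Should an event have a missing severity or relationship, it will be classified as having the highest severity and/or strongest relationship".

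The cost is a short addition to the definition, a little programming and possibly some site queries. The downside is slightly higher reported TEAE rates, since the fallback will admit some events that did not worsen on drug.

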
Vicinium 30 mg in 50 mL of saline will be administered intravesically through the catheter. After complete administration of the Vicinium dose, the catheter may be clamped and remain in for the 2-hour dwell time, or it may be removed, per the discretion of the investigator. Subjects will be instructed to hold the study drug in the bladder for 2 hours. During this time, subjects will be required to the best of their ability, to position themselves upright (standing or sitting), prone, supine, and in the left and right lateral decubitus positions for at least 15 minutes each, in any order. After 2 hours, the bladder will be drained and the catheter removed (if the catheter remained in place) or the subject will void to empty their bladder. The subject must remain at the clinic for the entire 2 hour dwell duration.
	

An appropriate local anesthetic and sterile lubricant may be used at the time of catheterization. In addition, an antibiotic may be given at the discretion of the Investigator.
	

Study Procedures: At each dosing visit, pre-dose and post-dose, vital sign measurements and adverse event assessments will be conducted. At the Screening cystoscopic assessment, visual mapping and recording of the position of tumors in the bladder must be performed, including quantification of the overall area of the bladder affected. Directed biopsies will be performed prior to the first dose to histologically confirm non-muscle invasive bladder cancer. Urine cytology will be performed prior to the last dose in the Induction Phase, and cystoscopy will be performed at the end of the Induction Phase. Cystoscopy and cytology will also be assessed every 13 weeks (3 months) during the Maintenance Phase. At each cystoscopic evaluation while the subject is on-study, directed biopsies should be taken from all areas of apparent disease or suspicious for disease, including any area of inflammation. When positive or suspicious cytology is observed in the case of negative cystoscopy, random bladder biopsies will be obtained from the locations of disease identified at Screening (i.e., by screening biopsies and the screening bladder mapping) and from other areas of the bladder so that all the following areas of the
	

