Of the 134 subjects,  $\geq 77$  will accrue to Cohort 1. Up to 57 additional subjects in total may accrue to Cohorts 2 and 3. This is an outpatient study. All treatments may be administered in the study clinic.

All diagnostic pathology (bladder tissue and urine cytologies and if performed, tissue from prostatic urethral biopsies) will be reviewed and graded by an independent pathologist and cytopathologist with experience in NMIBC diagnoses. The details of sample handling and logistics will be provided in a separate laboratory manual.

The sample used for determining subject eligibility for inclusion into the trial (post-BCG biopsy) must be reviewed and signed off by the pathologist prior to study enrollment and start of study treatment. All other samples will be read in a timely fashion and the results will be available to study investigators via the electronic CRF.

[figure not shown]
Time points for this study will use a week–day convention. For each subject, Day 1 is defined as the date that the subject first receives study drug and will be designated as Week 1 Day 1 (W1D1). The day before this date is Day  $-1$  (W $-1$ D $-1$ ; there is no Day 0).

Each subject's study course consists of a Screening Period, a 12-week Induction Phase, a Maintenance Phase and a Post-Treatment Evaluation. Subjects will receive intravesical Vicinium instillations twice weekly (BIW) for 6 weeks followed by once weekly for 6 weeks for a total of 18 doses in the Induction Phase. The twice-weekly doses are to be administered at least 48 hours apart (and no more than 2 doses may be administered within a calendar week, i.e., within a Sunday through Saturday). During the Maintenance Phase, Vicinium is administered once every other week. Total duration of treatment (combined Induction and Maintenance Phases) is up to 2 years (104 weeks). Subjects with a protocol-defined treatment failure (see [Section 14.2](#)) or other criteria for study drug discontinuation (see [Section 11.3](#)) will be withdrawn from the study.

[figure not shown]
Subjects will be evaluated for disease every 13 weeks ([Figure 1](#), [Section 10.4](#), [Section 10.5](#)). The first on-study evaluation will occur after the Induction Phase. At Week 12, a urine sample for cytology will be collected. In Week 13, subjects will undergo cystoscopy. Subjects without

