### 10.4 Post-Induction Phase Evaluation

Subjects will be evaluated for disease status at the end of the Induction Phase. Urine cytology is obtained in week 12 as described above. Starting in week 13 (or as soon as possible after week 12) subjects will undergo cystoscopy and directed biopsies/TURBT of all lesions suspicious for disease. Subjects are eligible to receive Maintenance Phase treatment if they do not have a protocol defined treatment failure (see [Section 14.2](#)) or other criteria for study drug discontinuation (see [Section 14.3](#)) and are tolerating treatment.

See [Section 14.4](#) for criteria to continue treatment.

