Subjects with CIS (Cohort 1 or Cohort 2) will be considered to have a complete response if at the time of any disease status evaluation (per protocol every 13 weeks or any unscheduled evaluation) there is no evidence of high-grade disease (CIS, high-grade Ta or any grade T1 disease) or disease progression (e.g., to muscle invasive disease). Subjects whose initial diagnosis was CIS who are found to have low-grade Ta disease at the time of an evaluation must have the low-grade disease resected by TURBT. Low-grade Ta disease is not considered a treatment failure in these subjects and they may remain on study treatment following TURBT.

Date of Complete Response or Treatment Failure

Given that the cystoscopy, biopsy, and cytology assessments may be conducted on different dates, the date of complete response or treatment failure will be defined as the earliest assessment date of these assessments.

Duration of Response

Duration of Response will be analyzed for subjects with CIS with or without papillary disease (Cohort 1 + Cohort 2) who achieve complete response using a Kaplan-Meier (KM) product-limit method. It is defined as the number of days from the date of first occurrence of complete response to the date of documented treatment failure or death, whichever occurs first. Subjects who do not experience treatment failure or death will be censored at their last assessment of response.

Event

For the purposes of defining Event-Free Survival, an event is defined as treatment failure or death on or prior to treatment discontinuation. Because disease assessments are not recorded after treatment discontinuation, a death after treatment discontinuation will not be counted as an event so as not to artificially inflate EFS. Presence of upper or lower urinary tract urothelial carcinoma and having a cystectomy are not treated as events for analysis but do trigger special data handling in the event-free survival analysis.

Event-Free Survival

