3.3.9. Combining Data Across Panels

When data are combined across panels to create composite endpoints, like complete response, information will be combined in the following manner:

1. Data will be merged by visit for each subject.
2. Unscheduled and early termination data will be windowed according to the visit windows below. Additionally, data from visits where pathology, cytology, and cystoscopy are unexpected (i.e., Maintenance Month 4) will be windowed using the table below.
3. Data within a given visit window will be collapsed to the worst-case result. For example, if a subject has two central pathology assessments for a given visit one with 'CIS' and the other with 'No Tumor', the analysis result for the collapsed visit will be considered as 'CIS'.
4. The date corresponding to the collapsed visit will be the earliest observed date for the visit.

Analysis Visit	Study Days
Screening	-8 < Study Day < 1
Week 1	1 <= Study Day <= 49
Post Induction Phase	49 < Study Day <= 137
Maintenance Month 3	137 < Study Day <= 227
Maintenance Month 6	227 < Study Day <= 318
Maintenance Month 9	318 < Study Day <= 409
Maintenance Month 12	409 < Study Day <= 500
Maintenance Month 15	500 < Study Day <= 591
Maintenance Month 18	591 < Study Day <= 682

Maintenance Month 21	682 < Study Day <= 773
Long-term Follow up Month 3	773 < Study Day <= 864
Long-term Follow up Month 6	864 < Study Day <= 955
Long-term Follow up Month 9	955 < Study Day <= 1046
Long-term Follow up Month 12	1046 < Study Day <= 1137
Long-term Follow up Month 15	1137 < Study Day <= 1228
Long-term Follow up Month 18	1228 < Study Day <= 1319
Long-term Follow up Month 21	1319 < Study Day <= 1410
Long-term Follow up Month 24	1410 < Study Day <= 1501

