- 14.2.2.4.1 Histogram of Maintaining CR for at Least 1 Year Post-Induction Phase for Subjects with CR at Months 3, 6, 9, and 12
- 14.2.2.4.2 Histogram of Maintaining CR for a Duration of at Least 1 Year for Subjects with CR at Months 3, 6, 9 and 12
- 14.2.2.5 Swim-Lane Plot: Duration of Response
- 14.2.3.2 Kaplan-Meier Plot: Event-free Survival
- 14.2.4.2.1 Kaplan-Meier Plot: Cystectomy-Free Days by Cohort
- 14.2.4.2.2 Kaplan-Meier Plot: Cystectomy-Free Days for Responders vs Non-Responders
- 14.2.5.2.1 Kaplan-Meier Plot: Time to Disease Recurrence – Cohort 3
- 14.2.5.2.2 Swim Lane Plot: Time to Disease Recurrence – Cohort 3
- 14.2.6.2 Kaplan-Meier Plot: Progression-free Survival
- 14.2.7.2 Kaplan-Meier Plot: Overall Survival
- 14.3.4.1.2 Spaghetti Plot: Clinical Laboratory Assessments by Visit – Subjects with a Treatment Emergent Grade 3 or Higher Event
- 14.3.4.1.3 Scatter Plot: Alanine Aminotransferase by Visit vs. Baseline
- 14.3.4.1.4 Scatter Plot: Alkaline Phosphatase by Visit vs. Baseline
- 14.3.4.1.5 Scatter Plot: Aspartate Aminotransferase by Visit vs. Baseline
- 14.3.4.1.6 Scatter Plot: Bilirubin by Visit vs. Baseline
- 14.3.4.1.7 Scatter Plot: Creatinine by Visit vs. Baseline
- 14.3.4.1.8 Scatter Plot: Hemoglobin by Visit vs. Baseline
- 14.3.4.1.9 Scatter Plot: Leukocytes by Visit vs. Baseline
- 14.3.4.1.10 Scatter Plot: Lymphocytes by Visit vs. Baseline
- 14.3.4.1.11 Scatter Plot: Neutrophils by Visit vs. Baseline
- 14.3.4.1.12 Scatter Plot: Platelets by Visit vs. Baseline

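### Response and failure are both dated at the earliest test of an evaluation, so duration of response starts about a week before the cystoscopy that supports it and some failures are dated to a negative test

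*SAP*

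**What the plan says.** **Dating rule.** SAP 3.3.7 recognises that cystoscopy, biopsy and cytology may fall on different days and resolves this with one rule for both ends of a response: "the date of complete response or treatment failure will be defined as the earliest assessment date of these assessments". For data combined across panels, SAP 3.3.9 first collapses each visit window to the worst result (step 3) and then dates it (step 4): "The date corresponding to the collapsed visit will be the earliest observed date for the visit". The Post-Induction window covers Days 50 to 137 and the Maintenance Month 3 window Days 138 to 227.

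**DoR.** It is "the number of days from the date of first occurrence of complete response to the date of documented treatment failure or death". Subjects without either event "will be censored at their last assessment of response". DoR is listed under the primary endpoints in SAP Section 2 and Protocol 9.1.

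**Order of tests.** Protocol Section 10: "At Week 12, a urine sample for cytology will be collected. In Week 13, subjects will undergo cystoscopy". The Synopsis adds: "Urine cytology will be performed prior to the last dose in the Induction Phase". Protocol 10.4 lets cystoscopy run later: "Starting in week 13 (or as soon as possible after week 12) subjects will undergo cystoscopy". In maintenance, Protocol 10.5 puts cystoscopy and cytology at the same nominal week, with a window of one week before to two weeks after. It also expects that repeat cytology, cystoscopy or biopsies may follow.

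**One-year display.** SAP Section 12 plans Figure 14.2.2.4.2, "Histogram of Maintaining CR for a Duration of at Least 1 Year". The SAP does not say how many days make a year.

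**The concern.** A negative cytology cannot establish complete response by itself. Protocol Section 14 (Table 6) requires cystoscopy at every evaluation, with biopsy of anything suspicious. Dating response at the first test therefore starts the clock before the evidence is complete. At the post-induction evaluation this gap is built into the schedule.

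It also affects nearly all responders. Under SAP 5.2.1, a subject who has failed once remains a failure at all later visits, and anyone who is neither a failure nor a discontinued subject with missing data is a responder. Almost every first response is therefore assigned at the post-induction visit.

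At the other end, steps 3 and 4 of SAP 3.3.9 together can attach a positive result to the date of an earlier negative test in the same window. That date enters DoR and, through the treatment failure date, event-free survival.

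The one-year mark is where a small shift shows most. Evaluations are 13 weeks apart, so Week 13 to Week 65 is 52 weeks, one day short of 365.

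**Working it through.** **Target days.** Day = (week − 1) × 7 + 1 gives 78 for Week 12, 85 for Week 13 and 449 for Week 65. These match the targets in SAP 3.3.8 (Week 65 appears there as Maintenance Month 12).

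**Start of response.** The nominal shift is 85 − 78 = 7 days. If an unscheduled test fell on Day 50, step 4 could move the start to 85 − 50 = 35 days before cystoscopy. No efficacy test is scheduled between Day 50 and Week 12, so this needs an unscheduled one.

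**Nominal DoR by failure visit.**

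| Failure at | From Week 12 cytology | From Week 13 cystoscopy |
|---|---|---|
| Week 26 (Day 176) | 98 | 91 |
| Week 39 (Day 267) | 189 | 182 |
| Week 52 (Day 358) | 280 | 273 |
| Week 65 (Day 449) | 371 | 364 |
| Week 78 (Day 540) | 462 | 455 |

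Only the Week 65 row crosses 365 days. Moving that visit within its window gives 364 versus 357 (one week early, both under), 378 versus 371 (one week late, both over) and 385 versus 378 (two weeks late, both over).

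**Share of Week 65 failures reaching 365 days.** Assumptions: cytology uniform on Days 78–84, Week 65 evaluation uniform on Days 442–469 (28 days), and cystoscopy uniform on Days 85–91 or Days 85–98. Counting all date pairs:

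- From cytology: 168 of 196 = 86%.
- From cystoscopy, Days 85–91: 119 of 196 = 61%.
- From cystoscopy, Days 85–98: 189 of 392 = 48%.

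The gaps equal the mean shift divided by the window: 7/28 = 25 points and 10.5/28 = 37.5 points.

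**Effect on responders.** Assume constant retention per evaluation of 0.5^(1/5) = 0.871. The share failing at Week 65, the fourth evaluation after Week 13, is 0.871³ − 0.871⁴ = 0.660 − 0.574 = 8.5%. Then 8.5% × 0.25 = 2.1 points and 8.5% × 0.375 = 3.2 points.

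**Failure end.** Suppose the Week 26 evaluation is clear on Day 176 and a for-cause biopsy on Day 225 shows carcinoma in situ. Both fall in the Day 138–227 window, so the collapsed result is failure dated Day 176, which is 225 − 176 = 49 days early. Under the SAP rule DoR is 176 − 78 = 98 days. From cystoscopy to the positive biopsy it is 225 − 85 = 140 days. Here the SAP rule shortens DoR by 42 days.

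**Net effect.** If a failure work-up runs L days from its first test to its last, then relative to dating both ends at the last test the SAP rule changes DoR by 7 − L days: +7 at L = 0, 0 at L = 7, −7 at L = 14. The documents give no value for L.

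**The case against.** The strongest reply is that one symmetric, disclosed rule covers both ends, and that an earliest-date rule for failure is conservative for DoR. This stands in part: maintenance work-ups can also be spread over days, so the effects may cancel or reverse. A reader might infer that the rule lengthens every DoR. The documents do not support that, as the Day 225 example shows. There is also no shift when the Week 12 cytology was missed or taken on the day of cystoscopy.

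The one-year crossing is fragile. It is a one-day margin against a 365-day year that the SAP does not define. The study calendar treats 104 weeks as two years, and on a 52-week year the nominal 364 days already qualifies. Counting inclusively (+1) also brings 364 to 365. A reader might infer that Week 65 relapses as a group are moved past one year. That is not so: early visits stay under and late visits are over either way.

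The consequence is also limited. DoR is a descriptive Kaplan-Meier estimate with no test and no named 12-month landmark, and 7 days is small beside a 13-week interval. Because the cytology is taken before dosing at the Week 12 visit, its date may be the same calendar day as the last induction dose, so nothing should be built on that order.

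Symmetry does not answer the core point, however. Response is dated before it can be known, and a failure can be dated to a day on which every result was negative. Two dating errors of opposite sign need not cancel within a subject.

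**Conclusion.** The dating rule needs correcting at both ends. On schedule it starts DoR about 7 days before the cystoscopy needed to establish response, and more if an unscheduled test falls earlier in the Post-Induction window. It can also backdate failure to a negative test, which shortens DoR and event-free survival. The direction of the net bias is not established.

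Under the uniform-date assumptions and the permitted visit window, 86% rather than 48–61% of Week 65 failures reach 365 days. That is about 2–3 points of responders at the assumed 8.5% failure share. Larger figures are tempting. If every evaluation fell inside Week 65 itself, the contrast would be 100% versus 21–43%, or about 5–7 points at the same 8.5%. That requires ignoring the window that Protocol 10.5 allows. None of these figures includes an offset from backdated failures.

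Complete response rates by visit do not depend on the date assigned to the result and are unaffected.

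**What to change.** In SAP 3.3.7, split the rule:

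- **Complete response:** the date of the last assessment needed to establish it at that evaluation (cystoscopy and cytology, plus biopsy or second cytology where required).
- **Treatment failure:** the date of the first central biopsy or cytology sample that is itself positive. SAP 3.3.7 also counts subjects discontinued for treatment failure or recurrence as failures. They may have no such sample, so name a date for them.

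Align SAP 3.3.9 step 4 with this, so that a collapsed result takes its date from the assessments that determine it. State the number of days in one year and whether DoR is counted inclusively.

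If the present rule is kept for the main analysis, add the split rule as a DoR sensitivity analysis. The two sensitivity analyses in SAP 5.2.3 do not address dating.

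The cost is SAP wording and derivation code, since the test dates are already collected. Individual durations may become slightly shorter or longer.
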